3.3.1 Three Group Comparative Analysis

A total of 84 subjects will be randomized to one of 3 healthy and nutritionally complete diets that differ only in the fatty acid composition of added visible oils. All foods will be provided through the NIH metabolic kitchen, with subjects visiting the kitchen daily Monday through Friday to obtain foods. Each Friday, subjects will carry home foods packed for their weekend meals. Baseline testing battery will include: 1) blood composition of omega-6 and omega-3 HUFA; 2) endocannabinoid, eicosanoid, and docosanoid derivatives of omega-6 and omega-3 HUFA; 3) insulin function assessment; 4) body composition assessment; 4) functional satiety assessment; and 5) self-reported measures of satiety, hunger and affective states. The full baseline testing battery will be repeated after 84 days of randomized treatment. An abbreviated testing battery will be performed after 28 and 56 days of randomized treatment. A subset of participants will undergo additional inpatient testing as described in Section 3.3.2. The remaining subjects will remain ambulatory throughout the study. Participants will be advised to continue their usual medical care and medications throughout the study.

3.3.2 36-week Continuation Sub Study

At completion of the 84 day (12 week) study, participants in the low LA group (Group B) will have the option of continuing their study diets for another 252 days (36 weeks). Continuing subjects will consume the same low LA (1 en%) diet. During the continuation phase, the abbreviated testing battery will be completed after 6, 12, 18, 24 and 30 weeks, and the full testing battery will be repeated after 36 weeks.

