5.2 Specific hypotheses

5.2.1A Primary aims

To evaluate the effects of modifying the dietary nutrient LA on the %omega-6 in HUFA; as well as two endocannabinoids derived from omega-6 PL-AA, 2-AG and AEA.

5.2.1B Primary hypotheses

Lowering dietary intake of LA as a controlled variable from 8% to 1% of daily food energy will significantly decrease the %omega-6 in HUFA and the endocannabinoid derivatives of omega-6 AA, 2-AG and AEA.

5.2.2A Secondary aims

To assess the effects of modifying the dietary nutrient LA on the rates of change in omega-6 and omega-3 HUFA, 2-AG, and AEA over time; adipose and muscle tissue fatty acid content, relevant metabolic mediators measured in plasma, body composition, functional satiety, and psychometrics, as follows.

Metabolic outcomes will include other endocannabinoids, eicosanoids and docosanoids derived from omega-6 and omega-3 HUFA, 24-hr energy metabolism, and endocrine hormones related to obesity.

Adipose and muscle tissue outcomes will include tissue concentrations of omega-6 and omega-3 HUFA. Body composition outcomes will include DEXA, 3T MRI, anthropometric measurements and bioelectrical impedance. Functional satiety will be assessed via (buffet-style) food array testing.

Psychometric outcomes will include self-reported measures of hunger, satiety, and affective states. Genotyping will also be performed to assess for interactions between selected gene variants and effects of the intervention.

5.2.2B Secondary hypotheses

Lowering dietary intake of LA as a controlled variable from 8 en% to 1 en% will result in:

- Increased omega-3 HUFA and reduced omega-6 HUFA in muscle and adipose tissue biopsies
- Reduced total fat content of adipose and muscle tissue biopsies
- Reciprocal increases in accretion of the omega-3 HUFA and their endocannabinoid, eicosanoid, and docosanoid derivatives.
- Favorable effects on insulin sensitivity and endocrine hormone function.
- Favorable effects on gene expression profiles.
- Favorable effects on hunger, satiety, and affective states.
- Increased functional satiety.
- Reduced adiposity and increased lean body mass.

6 Subjects

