7.4 Study Design

We anticipate that 84 subjects will need to complete the baseline phase and be randomized, with an anticipated dropout of about 20 subjects during the diet phase, in order for 64 subjects to complete the 12-week diet phase. Based on previous NIH Clinical Center dietary protocols with a similar baseline phase, we anticipate that 30 to 55% of enrolled subjects will not complete the baseline phase due to lack of attendance, non-compliance with 7-day food records, and/or discovery of an underlying exclusionary condition during the baseline phase history, physical examination or laboratory testing. Therefore, *up to* 180 subjects will be enrolled in the baseline phase so that a sufficient number of subjects (64) will complete the diet phase.

After completing the baseline phase, 84 subjects will be randomized to 1 of 3 diets (Table 3), to be maintained for 12 consecutive weeks. We anticipate that about 20% of subjects will dropout during the diet phase. Therefore 64 subjects are expected to complete the diet phase.

Table 3: Fatty Acids in 3 Study Diets

Diet Group	omega-6 LA*	omega-3 ALA	omega-6 AA	omega-3 HUFA	%omega-6 in HUFA**
A. Orange	8.00	0.40	0.045	0.045	80
B. Blue	1.00	0.40	0.045	0.045	50
C. Green	1.00	0.40	0.045	0.81	20

*Fatty acid intake as percentages of daily food energy (en%).

** Predicted percentage of omega-6 HUFA in total omega-6 and omega-3 HUFA, via the Lands empirical equation, as detailed in Appendix 2

Please see Section 7.1: Study overview and design and Appendix 1: Study Design Flow Diagram.

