7.6.3 Specimen collection for biomarker testing

Blood Collection

To assess the blood compositions of omega-6 and omega-3 fatty acids and their metabolic derivatives, fasting venous blood will be collected at 4 timepoints in the main study (Baseline Visit 3; Diet Phase Visits 1, 2 and 3). Blood will be collected from participants in the optional continuation phase at 6 additional time points (see Table 5: Continuation Phase Visits). Blood will be immediately processed and stored at -80 degrees C. See Table in Appendix 2 for a list of fatty acids and their metabolic mediators that will be assessed.

Genotyping

This project will collect DNA samples from the saliva of well phenotyped overweight subjects for genotyping. Genotyping will be performed on all study participants. Single gene mutations/polymorphisms of interest include: 1) those involved in fatty acid metabolism; 2) those implicated in the pathogenesis of obesity; 3) those implicated in the pathogenesis of medical and psychiatric conditions associated with obesity; 4) those linked to certain behavioral characteristics relevant to obesity and obesity-related comorbidities. On the consent form, participants can designate whether or not the DNA samples can also be stored for future research projects.

Muscle and adipose tissue biopsies and tissue procurement and post-biopsy pain assessment

Fat and muscle biopsies will be obtained before and after the dietary interventions, by the study physicians and/or nurse practitioner. In accordance with established NIDDK practices, biopsies will be performed on the Metabolic Unit or the adjacent 5SW day hospital, as described below.

Subcutaneous adipose tissue (3-5 g) will be removed from the abdominal region by aspiration with a 16-gauge needle under local anesthesia (e.g. 2% xylocaine).

Muscle biopsies (100-250 mg) will be obtained under local anesthesia from the vastus lateralis, as follows. The patient will be prepped and draped in sterile fashion. The muscle biopsy procedure involves numbing a nickel-sized portion of the skin of the thigh with a local anesthetic and making a small incision, approximately 1/4 inch. The biopsy needle is then inserted via the incision through adipose tissue and muscle fascia into the muscle. A small sample of muscle tissue is removed. The incision will then be closed with steri-strips and covered with a dressing. If the muscle is too deep to be reach, the muscle biopsy will not be attempted.

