11.1 Overview

This study is a three-arm dietary intervention trial with a baseline measurement and with repeated measures of the outcome variables over time. The primary aim is to measure the pre- post- changes in our primary outcome variables: %omega-6 in HUFA, 2-AG and AEA. In secondary Aim 1, we will measure the rates of change in our primary outcome variables. Exploratory aims will be directed towards the extent and rates of change in our secondary outcome variables (see Section 10.2) in response to dietary interventions.

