11.2 Analysis of Data

Fatty acid concentration data will be examined for homogeneity of variance and normality of distribution, and if necessary transformed to meet this criterion. A probability of 0.05 or lower will be considered significant.

Primary Aim: The sample size was selected to provide adequate power (0.8) to test our Primary Aim, as described in section 11.3. In this Aim we plan to assess the extent of changes in %omega-6 in HUFA; 2-AG and AEA; after 84 days of targeted dietary interventions. To achieve this aim we will treat the data coming from a four-group (control and two treatment groups), pre-post study design. There will be a measurement for all the individuals in the study at randomization and at 84 days. The outcome will be the measurement at 84 days.

Secondary Aim 1: To assess the rate of changes in %omega-6 in HUFA; PL-AA; 2-AG and AEA; PL-EPA; and PL-DHA, we will make use of the repeated measures of the outcome variables measured at baseline, and 28, 56 and 84 days into the diet phase. The goal is to compare the rates of change in these outcome variables over time in the three groups. It is expected that the rates of change will be fastest in Group C (the low LA plus omega-3 HUFA diet group).

Exploratory Aims: Additional exploratory analyses will be performed to further examine the metabolic and clinical effects of dietary interventions by: 1) assessing the extent and rates of change of the *other* metabolic mediators and clinical outcome measures, as detailed in Section 10; 2) examining the association between the changes in blood concentrations of fatty acid precursors (e.g. PL-AA) and their metabolic derivatives (e.g. 2-AG); 3) examining the association between changes in precursor fatty acids and clinical outcome measures; and 4) examining the association between changes in the metabolic derivatives of precursor fatty acids and clinical outcome measures.

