11.3 Estimation of Power and Sample Size

We will use one-way analysis of variance to compare the proportion of %omega-6 in HUFA measured at 12 weeks among three groups. Assuming that the %omega-6 in HUFA will be, on average, 0.8, 0.5 and 0.2 in the three groups at the end of the 12 weeks (as predicted by Lands' empirical equation and the nutrient intake targets), we calculated required sample size at three values of standard deviation: the maximum value of 0.5, at 0.4 and 0.3. These values translate to root mean square standardized effect is calculated as 0.6, 0.75, and 1.0. To detect these effect sizes, at a power of 80% and an alpha of 0.05, we will need either 15 individuals per group ($s = 0.5$), 10 ($s = 0.4$), or 6 ($s = 0.3$).

Fig. 6. Sample Size and Power Curve

12 Human Subjects protection

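### The baseline value has no stated role in the primary analysis, and no test at all is named for 2-AG or AEA

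*Combined protocol and SAP*

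**What the plan says.** Three parts of the combined protocol and SAP bear on the primary analysis.

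- **11.1 Overview** frames the aim as change: "The primary aim is to measure the pre- post- changes in our primary outcome variables", namely %omega-6 in HUFA, 2-AG and AEA.
- **11.2 Analysis of Data, Primary Aim**, calls the design pre-post and says "There will be a measurement for all the individuals in the study at randomization and at 84 days". The next sentence fixes the analysis variable: "The outcome will be the measurement at 84 days". No model, covariate or change score follows.
- **11.3 Estimation of Power and Sample Size** contains the only test named for a primary outcome: "We will use one-way analysis of variance to compare the proportion of %omega-6 in HUFA measured at 12 weeks among three groups". No test, SD or effect is given for 2-AG or AEA.

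The baseline data will exist. The baseline battery in 3.3.1 includes "2) endocannabinoid, eicosanoid, and docosanoid derivatives of omega-6 and omega-3 HUFA", and 7.6.3 says "fasting venous blood will be collected at 4 timepoints in the main study", the first being Baseline Visit 3. Section 11.2 uses baseline explicitly only in Secondary Aim 1, on rates of change, where no model is named either.

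**The concern.** Read together, these sections leave three analyses open for each primary outcome: a Day-84 ANOVA, a change-score comparison, or a baseline-adjusted comparison. The aim in 11.1 points to change, the outcome in 11.2 is the Day-84 value, and the test in 11.3 has no baseline term. The three analyses differ in precision, and leaving the choice open allows it to be made after the data are seen.

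The stake is greatest for 2-AG and AEA. They are two of the three primary outcomes, they have no power basis, and only about 21 completers per arm are expected.

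**Working it through.** **Inputs from the documents.** Assumed 12-week means 0.8, 0.5 and 0.2; SDs 0.5, 0.4 and 0.3; alpha 0.05; power 80% (11.3). Randomized 84, completers 64 (7.4), so 84/3 = 28 randomized and 64/3 ≈ 21 completers per arm.

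**Assumed.** The baseline-to-Day-84 correlation r is not in the documents. I use 0.3, 0.5 and 0.7.

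**1. Reproducing 11.3.** For the three-group F test, λ = n·Σ(μᵢ − μ̄)²/SD², with Σ(μᵢ − μ̄)² = 0.3² + 0 + 0.3² = 0.18 and df 2 and 3(n − 1).

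| SD | Stated n per group | λ | Power |
|---|---|---|---|
| 0.5 | 15 | 15 × 0.18/0.25 = 10.8 | 0.82 |
| 0.4 | 10 | 10 × 0.18/0.16 = 11.25 | 0.82 |
| 0.3 | 6 | 6 × 0.18/0.09 = 12.0 | 0.81 |

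The stated sizes reproduce, so 11.3 was sized on an ANOVA of Day-84 values without a baseline term.

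**2. %omega-6 in HUFA, three-group test, 21 per arm.** Unadjusted, λ = 15.1, 23.6 and 42.0 at SD 0.5, 0.4 and 0.3 (df 2 and 60), giving power 0.93, 0.99 and >0.999. Adjustment multiplies the error variance by (1 − r²) and uses one error df. At SD 0.5, power becomes 0.95, 0.98 and 0.999 at r = 0.3, 0.5 and 0.7.

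**3. 2-AG and AEA, detectable differences in SD units.** Two-sided 0.05, 80% power, 21 per arm. A-B uses the noncentral t with noncentrality δ√(n/2) and three-group error df 60. With the covariate, δ is divided by √(1 − r²) and df is 59. For a change score the SD is multiplied by √(2(1 − r)).

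| Analysis | r = 0.3 | r = 0.5 | r = 0.7 |
|---|---|---|---|
| A-B, Day-84 only | 0.88 | 0.88 | 0.88 |
| A-B, change score | 1.04 | 0.88 | 0.68 |
| A-B, ANCOVA | 0.84 | 0.76 | 0.63 |
| Three-group test, B and C equally shifted from A, Day-84 only | 0.85 | 0.85 | 0.85 |
| Three-group test, same pattern, ANCOVA | 0.81 | 0.74 | 0.61 |

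At r = 0 the ANCOVA figure for A-B is again 0.88. Two-group error df (40, or 39 with the covariate) barely changes A-B: 0.89 unadjusted and 0.85, 0.77 and 0.63 adjusted.

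In sample-size terms, 21/(1 − r²) = 21/0.91, 21/0.75 and 21/0.51, or about 23, 28 and 41 unadjusted completers per arm. This is an equivalence in precision only; it does not recover women who leave.

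**4. A-B for %omega-6 in HUFA.** The primary hypothesis is about "Lowering dietary intake of LA as a controlled variable from 8% to 1% of daily food energy", which is diet A against diet B. Section 11.3 sizes the three-group test instead. For the planned difference of 0.8 − 0.5 = 0.3, unadjusted A-B power is 0.48, 0.67 and 0.89 at SD 0.5, 0.4 and 0.3. At SD 0.5, adjustment raises it to 0.52, 0.60 and 0.76 for the three values of r.

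The pilot table in 4.3 implies a much smaller SD. The week-12 interval 60.3 to 69.0 with n = 18 gives (8.7/2) × √18/2.110 ≈ 8.7 percentage points. At that SD the planned 30 points is about 3.4 SD, and A-B power exceeds 0.99. Those data are from erythrocytes with diets pooled, so this is only a guide.

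**The case against.** **The wording may already imply ANCOVA.** Naming the post-treatment value as the outcome of a pre-post design is also how a baseline-adjusted analysis might be described. The ANOVA appears only in the sample-size section, and sizing on a simpler test is common. An intended ANCOVA cannot be ruled out. But it is not written, and the same words fit a change score or the ANOVA that 11.3 does name.

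**The harm is not demonstrated.** This largely stands. The Day-84 ANOVA is valid, the loss for %omega-6 in HUFA is probably negligible, and at r = 0.3 the gain for 2-AG and AEA is worth about two women per arm. What does not depend on r is that two of the three primary outcomes have no named test.

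**A-B power at SD 0.5 is a worst case.** That is fair: 11.3 calls 0.5 the maximum, and power is better at its other SDs and at the pilot SD. Sizing the A-B contrast is also a different question from using baseline. It matters here only because the rewritten analysis must say which comparison is primary.

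**An ANCOVA of women with a Day-84 value sidesteps dropout.** This stands. Section 7.4 plans the trial "with an anticipated dropout of about 20 subjects during the diet phase", which is 20/84 = 24%, although the same section also says about 20%. Baseline adjustment does not repair bias from those losses. A repeated-measures model using Days 28 and 56 is another option, but missing data need their own decision.

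**Conclusion.** The concern holds. The plan gives the collected baseline value no stated role in the primary analysis, names an unadjusted test for one primary outcome and none for the other two, and does not reconcile change in 11.1 with the Day-84 value in 11.2.

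This is an avoidable gap in specification with a possible loss of precision. It does not make the randomized comparison invalid. For 2-AG and AEA, the avoidable widening of the detectable A-B difference runs from nothing at r = 0, through 0.04 SD at r = 0.3, to 0.25 SD at r = 0.7. These figures assume equal arms of about 21 completers and an r that the documents do not supply. The plan should be changed because the remedy is nearly free. Confidence in the practical size is moderate, since it depends on r.

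**What to change.** In 11.2, state:

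> For each of %omega-6 in HUFA, 2-AG and AEA, the Day-84 value (transformed if needed) will be analysed by ANCOVA with the three-level diet group as factor and the same outcome's value at randomization (same transformation) as covariate, in all randomized women with a Day-84 value, in the group assigned. The baseline-adjusted three-group test is primary. The adjusted A-B difference with 95% CI will also be reported.

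This keeps the three-group comparison that 11.3 sizes and adds the contrast the primary hypothesis asks about. In Table 3, diets A and B have the same omega-3 HUFA and differ in LA, whereas C also raises omega-3 HUFA.

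Consequential edits:

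- In 11.1, replace the change wording with the baseline-adjusted difference between diets at Day 84.
- In 11.3, say that the sample size is for the unadjusted three-group test on %omega-6 in HUFA and does not size A-B.
- In 11.2, correct the reference to four groups; the text lists one control and two treatment groups.

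The cost is wording and one degree of freedom per model. No new blood draw or assay is needed, and if r is near 0 there is little gain. A-B remains weaker than the three-group test at SD 0.5. Bias from dropout, and how the 0.05 level applies across three primary outcomes, are separate matters that this change does not settle.

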11.3 Estimation of Power and Sample Size

We will use one-way analysis of variance to compare the proportion of %omega-6 in HUFA measured at 12 weeks among three groups. Assuming that the %omega-6 in HUFA will be, on average, 0.8, 0.5 and 0.2 in the three groups at the end of the 12 weeks (as predicted by Lands' empirical equation and the nutrient intake targets), we calculated required sample size at three values of standard deviation: the maximum value of 0.5, at 0.4 and 0.3. These values translate to root mean square standardized effect is calculated as 0.6, 0.75, and 1.0. To detect these effect sizes, at a power of 80% and an alpha of 0.05, we will need either 15 individuals per group ($s = 0.5$), 10 ($s = 0.4$), or 6 ($s = 0.3$).

Fig. 6. Sample Size and Power Curve

12 Human Subjects protection

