4.3 Translation from rats to humans

Do these principles apply to humans?

Like rodents, humans lack the enzymatic machinery to synthesize AA *de novo*. Thus, human tissue concentrations of PL-AA and other omega-6 HUFA are dependent upon dietary consumption of AA; its precursor-LA; and omega-3 acids that compete with omega-6 acids for enzymatic elongation, desaturation, acylation, and incorporation into human tissue phospholipids (17). Competition continues as omega-6 and omega-3 HUFA act as rival substrates for enzymatic cleavage and conversion into omega-6 and omega-3 endocannabinoids. Therefore, as in rodents, the reduction of dietary LA is a plausible strategy for decreasing tissue PL-AA and its endocannabinoid derivatives in *human* tissues.

Pilot data from the combined analysis of the first 20 participants in a randomized dietary trial testing the effects of a 12-week reduction of dietary LA, found that AA declined significantly, and EPA+DHA increased significantly, with or without added EPA+DHA (Table 2). These data indicate that 12 weeks is sufficient to detect significant changes in AA, EPA, and DHA. However, dynamic equilibrium in erythrocyte fatty acids was not reached between weeks 8 and 12 weeks.

Table 2. Means of erythrocyte fatty acids over the 12-week intervention, Chronic Daily Headache study, May 2010

Variable	Baseline (n=20)		Week 4 (n = 20)		Week 8 (n=20)		Week 12 (n=18)	
	Mean	95% CI	Mean	95% CI	Mean	95% CI	Mean	95% CI
Omega-3 index	4.4	3.9, 5.0	6.2	5.4, 7.1	7.0	5.9, 8.1	7.8	6.5, 9.0
Omega-6 in HUFA	76.3	74.5, 78.0	70.4	67.5, 73.2	67.4	63.7, 71.0	64.7	60.3, 69.0
DHA	4.0	3.5, 4.5	5.2	4.5, 5.8	5.7	4.9, 6.5	6.3	5.4, 7.3
EPA	0.46	0.39, 0.54	1.1	0.8, 1.3	1.3	0.95, 1.6	1.4	1.0, 1.8
AA	14.8	14.5, 15.2	14.4	13.7, 15.1	13.8	13.2, 14.5	13.7	12.9, 14.5
LA	11.5	10.8, 12.1	9.5	8.8, 10.2	9.3	8.6, 10.0	9.5	8.8, 10.3

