We will use a t-test to compare the synthesis-secretion rates and coefficients measured at 4 weeks in the two groups (A and B). Assuming a 20-30% standard deviation in the synthesis-secretion rates based on our prior kinetic work in humans (74) and rodents (64) and a 67% difference in expected change in kinetics consistent with Pawlosky et al (74) and prior measured changes in DHA concentrations, we calculated required sample size(s) (Fig. 10). To detect these effect sizes, at a power of 80% and an alpha of 0.05, we will need 4-12 individuals per group.

Fig. 10. Sample Sizes for Endogenous DHA Synthesis Amendment

Sample Size Calculation (Spreadsheet1)	
Two Means, t-Test, Ind. Samples	
H0: Mu1 = Mu2	
Population Mean Mu1	14.1000
Population Mean Mu2	23.5470
Population S.D. (Sigma)	7.7620
Standardized Effect (Es)	-1.2171
Type I Error Rate (Alpha)	0.0500
Critical Value of t	2.0739
Power Goal	0.8000
Actual Power for Required N	0.8130
Required N (per group)	12.0000

Sample Size Calculation (Spreadsheet1)	
Two Means, t-Test, Ind. Samples	
H0: Mu1 = Mu2	
Population Mean Mu1	14.1000
Population Mean Mu2	23.5470
Population S.D. (Sigma)	6.4684
Standardized Effect (Es)	-1.4605
Type I Error Rate (Alpha)	0.0500
Critical Value of t	2.1199
Power Goal	0.8000
Actual Power for Required N	0.8284
Required N (per group)	9.0000

Sample Size Calculation (Spreadsheet1) Two Means, t-Test, Ind. Samples H0: Mu1 = Mu2	
	Value
Population Mean Mu1	14.1000
Population Mean Mu2	23.5470
Population S.D. (Sigma)	3.7647
Standardized Effect (Es)	-2.5094
Type I Error Rate (Alpha)	0.0500
Critical Value of t	2.4469
Power Goal	0.8000
Actual Power for Required N	0.8386
Required N (per group)	4.0000

S11. Human Subjects protection – Infusion Substudy

For human subjects protection issues that apply to both the main protocol and the Infusion Substudy, please see Section 12 (Page 38) of the main protocol. Additional issues that apply to the Infusion Substudy are addressed in the following sections.

Justification of sensitive procedures

Procedures that may cause some discomfort to subjects:

Prolonged fast for d5-LNA Infusion: Participants are required to fast for up to 16 continuous hours. Participants will be provided with IV fluids but are likely to experience some hunger during the 8-hour infusion. They will be provided with a meal immediately after infusion.

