Appendix 1: Study Flow Diagram

Appendix 2: Lands Equation for Predicting Percentage of omega-6 in HUFA (%omega-6 in HUFA)

In a series of human experiments, Lands et al. assessed the relationships between 18, 20, and 22 carbon omega-6 and omega-3 fatty acid composition of diets, within typical U.S. dietary ranges, and percentages of omega-6 and omega-3 HUFA in total HUFA (17). Within these ranges, tissue accumulation of omega-6 and omega-3 HUFA were surprisingly consistent with the principles that Mohrhauer and Holman observed in rats. By combining human and animal data, Lands developed empirical equations relating fatty acid composition of diet to tissue HUFA content.

Lands' equation for tissue HUFA maintenance as a function of diet:

$$\% \omega-6 \text{ in HUFA} = \frac{100}{1 + \frac{HC_6}{en\%H6} \left(1 + \frac{en\%H3}{HC_3} \right)} + \frac{100}{1 + \frac{PC_6}{en\%P6} \left(1 + \frac{en\%P3}{PC_3} + \frac{en\%H3}{HI_3} + \frac{en\%O}{C_0} + \frac{en\%P6}{Ks} \right)}$$

where $HC_3=3.0$, $HC_6=0.70$, $PC_3=0.0555$, $PC_6=0.0441$, $HI_3=0.005$, $HI_6=0.040$, $C_0=5.0$, $Ks=0.175$.

The Lands equation accurately predicts mean population omega-6 and omega-3 HUFA proportions in populations with radically different dietary omega-6 and omega-3, supporting validity of the equations. Mean tissue percentages of omega-6 in total HUFA (%omega-6 in HUFA) varied widely, from less than 30% to more than 80% of total HUFA, in populations consuming dissimilar diets.

TABLE 1. Mean % ω -6 in HUFA in worldwide populations

Location	Mean % ω -6 in HUFA
Ohio, U.S.A	87
Detroit, U.S.A	82
Quebec (Urban)	78
Japanese Americans	70
Southern Spain	60
Japan (Urban)	47
Quebec (Inuit)	44
Japan (Rural)	34
Greenland	32

In a recent study, the %omega-6 in HUFA measured in whole blood correlated closely with liver, heart, and brain HUFA status in autopsied rats and pigs (75). In this respect, %omega-6 in HUFA outperformed other HUFA biomarkers including erythrocyte EPA+DHA, which did not correlate with EPA+DHA content of any of these tissues (75). Thus, the demonstration that the empirical equation of Lands accurately predicts changes in %omega-6 in HUFA in blood following major reductions in dietary intakes of LA would have important implications for any condition affected by membrane AA content, or any disease in which AA-derived mediators have been implicated, no matter which tissues are involved in the disease process.

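### The only primary test named is a three-diet ANOVA; the hypothesis about lowering LA alone (diet A vs diet B) has no named test, and the stated 80% power is not for it

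*Combined protocol and SAP*

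**What the plan says.** Section 5.2.1B states the primary hypothesis: "Lowering dietary intake of LA as a controlled variable from 8% to 1% of daily food energy will significantly decrease the %omega-6 in HUFA". It makes the same claim for the endocannabinoids 2-AG and AEA. Sections 3.1 and 5.1 make clear that the LA removed is replaced by oleic acid.

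Table 3 in section 7.4 gives the diets. A has LA 8 en% and omega-3 HUFA 0.045 en%. B has LA 1 and omega-3 HUFA 0.045. C has LA 1 and omega-3 HUFA 0.81. Of 84 women randomized, section 7.4 plans for 64 completers: "Therefore 64 subjects are expected to complete the diet phase".

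Section 11.2 describes the primary analysis as pre-post, with the Day 84 value as outcome. It counts four groups while listing a control and two treatments. It names no test and no comparison between particular diets. On power it says: "The sample size was selected to provide adequate power (0.8) to test our Primary Aim, as described in section 11.3".

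Section 11.3 names the test: "We will use one-way analysis of variance to compare the proportion of %omega-6 in HUFA measured at 12 weeks among three groups". It assumes means of 0.8, 0.5 and 0.2, takes the SD at "the maximum value of 0.5, at 0.4 and 0.3", and arrives at 15, 10 or 6 women per group for 80% power at alpha 0.05.

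The infusion substudy (S10) asks about the same 8-to-1 en% change, for DHA synthesis, and specifies a two-group t-test of A against B sized on that difference.

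**The concern.** The hypothesis concerns one change, LA for oleic acid, and one pair of diets carries it. A one-way ANOVA asks whether any of three means differ. Its answer can be driven by diet C, in which LA reduction is combined with an 18-fold rise in omega-3 HUFA (0.81/0.045). A significant F would therefore not show that lowering LA works.

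Two things follow. With no contrast written into section 11, A–B, A–C, B–C and A against B and C pooled all remain open, across three primary outcomes. And the 80% power that section 11.2 attaches to the Primary Aim belongs to the omnibus test, which benefits from the 0.6 gap between A and C, whereas the hypothesis rests on a gap of 0.3.

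The section is also silent on 2-AG and AEA, with no named test and no power inputs, and on whether success needs all three primary outcomes or any one.

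**Working it through.** **Inputs.** Means A 0.8, B 0.5, C 0.2; SD 0.5, 0.4, 0.3; n per group 15, 10, 6; alpha 0.05 (all section 11.3). Completers 64 (section 7.4), about 21 per diet. Equal allocation and a two-sided A–B test are my assumptions.

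**1. The plan's own figure.** The sum of squared deviations of the means from 0.5 is 0.3² + 0 + 0.3² = 0.18. The root mean square standardized effect is √(0.18/2)/SD = 0.3/SD = 0.6, 0.75, 1.0, as stated. The omnibus noncentrality is n × 0.18/SD² = 10.8, 11.25, 12.0, with 2 and 3(n − 1) df. The section 11.3 sample sizes reproduce.

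**2. A versus B on the same inputs.** The difference is 0.8 − 0.5 = 0.3. The noncentrality of the two-sample t is 0.3/(SD × √(2/n)).

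| SD | n per group (plan) | Omnibus F power | A–B power | A–B power at 21 per group | n per group for 80% A–B power |
|---|---|---|---|---|---|
| 0.5 | 15 | 0.817 | 0.355 | 0.475 | 45 |
| 0.4 | 10 | 0.817 | 0.355 | 0.660 | 29 |
| 0.3 | 6 | 0.805 | 0.347 | 0.885 | 17 |

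Testing A–B as a contrast with the pooled three-group error term barely changes the values at the plan's n (0.362, 0.366, 0.368).

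**3. Are those SDs credible?** A quantity between 0 and 1 with mean 0.8 has SD at most √(0.8 × 0.2) = 0.40; with mean 0.5 the ceiling is 0.50. The pooled A–B SD therefore cannot exceed √((0.16 + 0.25)/2) = 0.45, so the 0.5 row is out of reach. Table 2 in section 4.3 gives a week-12 pilot 95% CI of 60.3 to 69.0 (n = 18). Half-width 4.35, divided by t(0.975, 17 df) = 2.11 and multiplied by √18, gives SD 8.75 points, or about 0.09.

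**4. A–B power at SD 0.09 and 21 per diet.** Power is above 0.99 for the plan's 0.30; 0.98 for the pilot's fall of 76.3 − 64.7 = 11.6 points; 0.80 for 8 points; and 0.42 for 5 points (an illustrative value, not taken from the documents). The pilot is indirect: erythrocytes, another trial, and diets with and without added EPA+DHA combined.

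**5. Can the F-test reject with no LA effect?** Put LA 8, ALA 0.40, AA 0.045 and omega-3 HUFA 0.81 en% into the Appendix 2 equation. The documents do not give the other fats, so I take 15 to 30 en%. At 15 en%:

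- First term: 100/(1 + (0.70/0.045)(1 + 0.81/3.0)) = 4.8
- Second term: 100/(1 + (0.0441/8)(1 + 0.40/0.0555 + 0.81/0.005 + 15/5 + 8/0.175)) = 45.3
- Sum: about 50, and also about 50 at 30 en%

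Diet A's own inputs give 78 to 79. So take means 0.8/0.8/0.5: no LA effect, with omega-3 alone moving C. The noncentrality is n × 0.06/SD². The F-test rejects with probability 0.36/0.36/0.35 at the plan's n, 0.49/0.69/0.91 at 21 per diet (SD 0.5/0.4/0.3), and above 0.99 at 21 per diet with SD 0.09.

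**The case against.** The strongest reply is that the hypothesis already fixes the pair. Section 5.2.1B speaks of LA as the single controlled variable, and in Table 3 only A and B differ in LA alone, so an analyst who holds to it has little room to choose another comparison. That is a fair reading of intent, and it is why the repair is simple. But section 11 is where the test is defined, and the test defined there is a different one.

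Second, the 0.35 power is at sample sizes the trial does not plan, and the less favourable figures at 21 per diet depend on SDs that are too large, one of them unattainable. This stands. Inadequate power for A–B on %omega-6 in HUFA has not been shown; at the pilot SD and the plan's 0.30 difference, power is above 0.99. It limits the finding to a misattributed power statement and does not reach 2-AG or AEA.

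Third, the no-LA-effect scenario borrows its value for C from an equation that itself contains an LA effect, and it needs an assumed figure for other fats. Accepted: it illustrates how the F-test can mislead and is not a forecast.

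Fourth, the ANOVA may be meant for all three primary outcomes, since section 11.2 treats them together. Possibly; the success rule and the A–B contrast would still be missing.

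Finally, making comparisons with C secondary is partly a matter of preference. The defect itself is cured by naming A–B; ranking C below it is the tidiest way to keep one primary question.

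**Conclusion.** The concern holds. As written, the analysis does not test the primary hypothesis, and the 0.8 power in section 11.2 belongs to another test. On the plan's inputs, A–B power is about 0.35 at the stated n, against about 0.81 for the omnibus F. At 21 completers per diet it is 0.48 to 0.89 across the plan's SDs, and probably much higher at a realistic SD. These figures assume equal allocation, a two-sided 0.05 test and the plan's predicted means. The mismatch between test and hypothesis depends on none of those assumptions, nor on the true SD. It must be corrected before the analysis, because a significant F could be reported as support for LA lowering when diet C's omega-3 produced it.

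**What to change.** In sections 11.2 and 11.3:

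- Name A versus B at Day 84 as the primary contrast for each primary outcome. Make comparisons involving C secondary; the three-group F-test can stay as supporting.
- Restate power for A versus B on %omega-6 in HUFA, using the planned completers and a justified SD and difference.
- Say plainly that 2-AG and AEA have no power calculation.
- State whether all three primary outcomes must succeed or any one suffices. If any one suffices, control alpha, for example by a fixed testing order.

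This is wording only: no added participants or procedures, and no change to N. The cost is candour about power. If the present SDs are kept, the stated power becomes 0.48 to 0.89 at 21 per diet, below the claimed 0.8 at SD 0.4 and 0.5. If any one outcome suffices, alpha control costs some power on the others.
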